8.3.8 Adverse Events of Special Interest

AESIs must be monitored on an ongoing basis. These events will be reported with narratives, allowing for the collection of additional information, as warranted. The following may be considered AESIs for this study:

- Significant liver chemistry changes that do not satisfy study drug stopping rules (see [Section 7.1.1](#) and [Section 13.2](#)). Cases of Hy's Law should be reported as SAEs.
- Suicidality as indicated by Type 3, 4, or 5 ideation on the C-SSRS (see [Section 7.1.3](#) regarding study drug stopping criteria for suicidality and [Section 8.2.6.1](#) regarding the C-SSRS). This safety finding will be reported as an AESI if it is not considered an SAE definition (e.g., resulting in hospitalization).
- Depression or anxiety that is moderate or severe (CTCAE Grade 2 or higher), as assessed by the Investigator (see [Section 7.1.4](#) regarding study drug stopping criteria for depression or anxiety). This will be reported as an AESI if it is not considered an SAE (e.g., resulting in hospitalization).
- Adverse events of adrenal insufficiency will be reported on a separate Adrenal Insufficiency Form. Additionally, symptoms of adrenal insufficiency will be reported as SAE if they necessitate parental GC administration by a health care professional and two of the following criteria are met: hypotensive (systolic blood pressure <100 mmHg); nausea or vomiting; severe fatigue; documented hyponatremia, hyperkalemia, or hypoglycemia. If hospitalization was required or the event of adrenal insufficiency is deemed to be an important medical event, life-threatening, results in a persistent or significant disability/incapacity or death, it should also be reported as an SAE.
 - For SAEs of adrenal insufficiency, records from the office of health care provider, emergency facility or hospital the following information should be obtained as source documents to provide the following information:
 - Was stress dosing employed prior to the adrenal insufficiency event? If yes, what were the GC dose and duration of dosing and the cause for stress dosing prior to seeking medical attention?
 - What type, dose and route of parental GC was administered and the duration of administration?

- What concomitant medications were administered?
- What clinical laboratory results are available?
- What AEs occurred?
- What was the duration of stay if admitted to the hospital?

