13.2.1.1 Actions

- Immediately discontinue study drug.
- Within 24 hours, report the event to the Sponsor or designated contract research organization and complete the AE eCRF (indicating that it is an AESI).
- If the event also meets the criteria for an SAE (see [Table 3](#)), complete the SAE fields in the eCRF.
- Request list of any medications taken in last 48 hours. Specifically question about medications that are known to increase liver enzymes, such as aspirin, acetaminophen, ibuprofen, naproxen, diclofenac, phenylbutazone, and any antibiotics.
- Perform liver chemistry follow-up assessments (see [Section 13.2.1.2](#)).
- Monitor the participant until liver chemistry test abnormalities resolve, stabilize, or return to baseline (see [Section 13.2.1.3](#)).
- If restart/rechallenge is not granted, permanently discontinue study drug and continue participant in the study for any protocol-specified follow-up assessments.

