8.3.22 Treatment-Emergent Adverse Events

All AE verbatim terms reported on the eCRFs will be coded using the Medical Dictionary for Regulatory Activities (MedDRA® version 23.0). Treatment-emergent adverse events (TEAEs)

are defined as any AEs that have an onset or worsening in severity on or after the first dose of double-blinded study drug until 30 days after the last dose of study drug. Non-TEAEs include those events occurred during the screening and/or GC conversion Period and after 30 days of the last dose of study drug. Non-TEAEs will be listed in AE listings but excluded from TEAE summaries.

Related AEs are those reported by investigators as possibly related, probably related, or definitely related to the study drug or GC regimen.

AESIs are events that do not meet SAE criteria but must be monitored on an ongoing basis as defined in Protocol Section 8.3.8 and identified in the AE eCRF page. Serious AEs (SAEs) are defined according to the National Cancer Institute Common Terminology Criteria for Adverse Events (CTCAE 2017) version 5.0, as described in Protocol Section 8.3.3.1. Adverse events

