13.1.2 Summary of TEAEs by System Organ Class and Preferred Term

In addition, TEAEs will be summarized by MedDRA SOC and PT. Each summary table will be presented by study period (i.e., Placebo-Controlled Treatment, and Open-Label Treatment) and treatment group as well as overall by treatment group. A subject experiencing multiple occurrences of an adverse event will be counted only once for each PT. Subjects with multiple PTs within a SOC will be counted only once for that SOC. The summaries will be presented for

the following; if a summary does not include more than 20 events, summaries by PT only (Section 13.1.3) may be deemed to be sufficient:

- TEAEs by SOC and PT
- Severe TEAEs by SOC and PT
- Study drug-related TEAEs by SOC and PT
- Severe Study drug-related TEAEs by SOC and PT
- AESIs by SOC and PT
- AESI of liver Events
- Serious TEAEs by SOC and PT
- Serious Study drug-related TEAEs by SOC and PT
- TEAEs leading to study drug discontinuation by SOC and PT
- TEAEs leading to death by SOC and PT

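### The AESI definitions conflict between protocol sections and with the SAP, and as worded they make the AESI tables undercount the events they are meant to show

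*SAP*

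**What the plan says.** **SAP.** Section 8.3.22 defines the category, by reference to Protocol 8.3.8: "AESIs are events that do not meet SAE criteria but must be monitored on an ongoing basis". The same sentence goes on to name the source: "and identified in the AE eCRF page". The section then defines SAEs by CTCAE version 5.0, citing Protocol 8.3.3.1. Section 13.1.2 plans AESI tables by system organ class and preferred term, plus one for "AESI of liver Events", by period and treatment group.

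**Protocol, liver.** Section 8.3.8 lists "Significant liver chemistry changes that do not satisfy study drug stopping rules" as the liver AESI and sends Hy's Law cases to SAE reporting. Appendix 13.2.1.1 covers events that do meet stopping criteria and tells the site to "complete the AE eCRF (indicating that it is an AESI"; if the event also meets SAE criteria, the SAE fields are completed as well. Section 7.1.1 says that changes short of the stopping criteria may still count as AESIs.

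**Protocol, psychiatric.** Sections 7.1.3, 7.1.4 and 8.3.8 make these findings AESIs only when they are not SAEs. Section 7.1.3 covers suicidal behaviour and ideation; 8.3.8 names Type 3 to 5 ideation only.

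**Protocol, adrenal.** Section 8.3.8 states: "Adverse events of adrenal insufficiency will be reported on a separate Adrenal Insufficiency Form". Section 7.1.5 records the diagnosis as an adverse event, puts the component signs, symptoms and laboratory findings on a separate CRF, and calls unexplained acute adrenal insufficiency an AESI with no condition on seriousness.

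**Protocol, reporting route.** Section 8.3.6 reports AESIs on the SAE Report Form.

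**The concern.** AESI tables exist so that a named risk can be compared between arms in one place. Liver chemistry elevation is a named risk of the drug, and the benefit-risk statement in Protocol 2.3.3 relies on being able to monitor it. Adrenal insufficiency is the obvious risk when an algorithm lowers the glucocorticoid dose in patients who lack cortisol. If the definition removes events because they are serious, or because they reach a stopping rule, the AESI count falls as events get worse. An arm with more possible Hy's Law or stopping-level events could then show fewer liver AESIs than the other arm. The texts also disagree with each other, so two careful programmers could produce different AESI tables from the same data.

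**Working it through.** The plan gives no figure to reproduce. The check sets the definitions side by side for each kind of event, then runs an illustrative count.

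1. **Non-serious liver event at stopping level.** In Protocol Table 3 these include ALT at or above 5x ULN, ALT at or above 3x ULN with symptoms, and ALT at or above 3x ULN persisting for 4 weeks; the table does not label them SAEs. Under 8.3.8 they are not AESIs. Under 13.2.1.1 they are flagged as AESIs. Section 7.1.1 points the same way as 13.2.1.1: if changes short of stopping may *still* be AESIs, those that reach it are too. SAP 8.3.22 joins two conditions, the 8.3.8 definition and identification on the AE eCRF page. This event fails the first and meets the second.

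2. **Possible Hy's Law case.** Table 3 makes ALT at or above 3x ULN an SAE when total bilirubin is at or above 2x ULN (more than 35% direct) or INR exceeds 1.5. Under 13.2.1.1 it carries both the AESI flag and the SAE fields. Under SAP 8.3.22 it is not an AESI. SAP section 3 says the SAP governs where the two documents are inconsistent on planned analyses, so the exclusion would probably prevail.

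3. **Serious suicidality, depression or anxiety.** Protocol and SAP agree that these leave the AESI category. The AESI tables therefore hold only the non-serious part. Suicidal behaviour is covered by 7.1.3 and not listed in 8.3.8.

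4. **Adrenal insufficiency.** Section 7.1.5 makes the unexplained acute case an AESI whatever its seriousness; SAP 8.3.22 removes it if serious. Section 8.3.8 puts the event on a separate form; 7.1.5 puts only the component findings there. The SAP names the AE eCRF page as AESI source and never names that form. It plans no dedicated on-study summary of adrenal insufficiency, although section 10.4.2.3 summarizes past hospitalizations for it.

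5. **The boundary itself.** SAP 8.3.22 separates AESIs from SAEs but anchors SAEs to the severity scale of Protocol 8.3.3.1. The seriousness criteria are in Protocol 8.3.2, and 8.3.3.1 itself warns that severity and seriousness differ.

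**Illustrative count for one arm.** The counts are assumed, not from the documents: 2 subjects with possible Hy's Law, 3 with non-serious ALT at or above 5x ULN, and 1 with ALT at 3 to 5x ULN only. All six are taken to be flagged as AESIs.

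| Rule used in programming | Sum | Liver AESI subjects |
|---|---|---|
| 8.3.8 wording, non-serious only | 1 | 1 |
| eCRF flag, non-serious only | 3 + 1 | 4 |
| eCRF flag alone | 2 + 3 + 1 | 6 |

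The SAP as worded supports the first or second row. The third arises only if its seriousness restriction is not applied.

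**The case against.** The strongest objection is that nothing severe goes unreported. Protocol 8.3.1 makes a test result that leads to study drug discontinuation a reportable adverse event, so stopping-level liver events enter the TEAE and discontinuation tables by arm, and the severe tables if so graded. Possible Hy's Law cases enter the serious TEAE tables, and SAP 13.2 plans a separate Hy's Law summary. A reader might infer that the worst cases are left out of the safety analysis; the documents do not support that. The laboratory tables only partly make up for the gap in the AESI tables: SAP Table 18 has a single ALT threshold, above 3x ULN, which does not separate 3 to 5x from 5x and above.

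A reader might also infer that liver events meeting stopping rules are definitely excluded, so that the example must show 1 subject instead of 6. That does not follow either. Section 13.2.1.1 puts the flag on the very page the SAP reads, and the 8.3.8 list is permissive. This is a contradiction with a range of outcomes, not a settled exclusion.

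A third inference would be that adrenal insufficiency sits on a form the SAP does not read. Section 7.1.5 records the diagnosis as an adverse event, and the SAP states: "All AE verbatim terms reported on the eCRFs will be coded using the Medical Dictionary for Regulatory Activities". No form is excluded, so a preferred-term row may well appear. What stands is that the source is not named and the protocol sections differ.

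Keeping AESIs non-serious does follow the protocol's own convention for psychiatric events, and 8.3.6 wants AESIs distinguished from SAEs. That is a reason to show the two separately within the category, not to drop one of them. C-SSRS ideation and behaviour have their own tables in SAP 13.6.2, but only if more than 5 subjects in any dose level answer yes. Finally, the last sentence of SAP 8.3.22 breaks off in the available text; it should be checked for wording that bears on AESIs.

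**Conclusion.** The concern holds for the AESI summaries. Three things are wrong as written. SAP 8.3.22 removes serious events from every AESI table, against Protocol 13.2.1.1 for liver events and 7.1.5 for unexplained acute adrenal insufficiency. Protocol 8.3.8 contradicts 13.2.1.1, and what 7.1.1 implies, on stopping-level liver events. The SAP defines SAEs by a severity scale and does not name the Adrenal Insufficiency CRF as a source.

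The size cannot be taken from the documents. On the assumed counts the liver AESI table shows 1, 4 or 6 of 6 subjects according to the rule programmed, so between none and 5 are missing from it. The effect is on the by-arm AESI counts. It does not reach the TEAE, serious TEAE, discontinuation or Hy's Law outputs. This should be corrected before the tables are programmed, but it does not threaten safety reporting as a whole.

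**What to change.** - **SAP 8.3.22:** define AESIs by event category regardless of seriousness, and define SAEs by Protocol 8.3.2 in place of the CTCAE severity scale in 8.3.3.1.
- **SAP 13.1.2 and 13.1.3:** show serious and non-serious sub-rows within each AESI category, and show adrenal insufficiency by arm.
- **SAP data sources:** name the form for each AESI category, including the Adrenal Insufficiency CRF, and say how the SAE Report Form route in Protocol 8.3.6 relates to the AE eCRF page.
- **Protocol 8.3.8:** reconcile its AESI reporting wording with 7.1.1, 7.1.3 (suicidal behaviour), 7.1.5, 8.3.6 and 13.2.1.1.

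These are reporting definitions only; no stopping rule changes. The cost is wording in a few sections and some programmed rows. The downside is that serious events appear in both the SAE and AESI tables, which a footnote can explain.

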8.3.23 Geographic Regions

Approximately 75 investigative sites will participate in this study. Three geographic regions will be classified by the countries where these study centers are located: United States, Europe, and rest of world.

8.4 Analysis Windows

Clinical visits may occur outside protocol-specified windows. Therefore, instead of relying solely on visit labels in the clinical database, analysis visits and their windows are defined using Enrollment Day or Study Day. For the purposes of data analysis and summary, assessments and/or measurements will be flagged based on the collection date/time that is closest to the protocol-scheduled time point (or Target Study Day). Analysis visit windows are presented in by type of assessments and/or measurements.

Table 12 Visit Analysis Windows (Clinic visits only)

Protocol Specified Visit Number	Analysis Visit	Reference Study Day	Target Study Day	Start (days)	Stop (days)
Visit 1 (Screening)	Screening	Enrollment Day	-114	low	-7
Visit 2	Week -12	Enrollment Day	-84	-6	15
Visit 3	Week -8	Enrollment Day	-56	16	50
Visit 4	Week -2	Enrollment Day	-14	51	high
Visit 5	Day 1	Study Day	1	-6	7
Visit 6	Week 3	Study Day	22	8	32
Visit 7	Week 6	Study Day	43	33	64
Visit 8	Week 12	Study Day	85	65	106
Visit 9	Week 18	Study Day	127	107	148
Visit 10	Week 24	Study Day	169	149	197
Visit 11	Week 32	Study Day	225	198	253
Visit 12	Week 40	Study Day	281	254	323
Visit 13	Week 52	Study Day	366	324	408
Visit 14	Week 64	Study Day	450	409	492
Visit 15 or Extension Visit 1	Week 76	Study Day	534	493	high or 575
Extension Visit 2	Week 88	Study Day	617	576	659
Extension Visit 3	Week 100	Study Day	701	660	785
Extension Visit 4	Week 124	Study Day	869	786	953
Extension Visit 5	Week 148	Study Day	1037	954	1121
Extension Visit 6	Week 172	Study Day	1205	1122	1289
Extension Visit 7	Week 196	Study Day	1373	1290	1457
Extension Visit 8	Week 220	Study Day	1541	1458	1625
Extension Visit 9	Week 244	Study Day	1709	1626	1793
Extension Visit 10	Week 268	Study Day	1877	1794	1961
Extension Visit 11	Week 292	Study Day	2046	1962	2129
Extension Visit 12	Week 316	Study Day	2213	2130	2228
Visit 16 or Extension Visit 13 (follow up)	Follow-up	Study Day		Last dose +1	Last dose +30

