4.1.1 Study Periods

This study will consist of the following periods:

- A \leq 45-day *Screening Period* for confirmation of eligibility
 - Optional A4 Screening Visit.
 - Screening information captured within 45 days of Day 1 in this study (particularly screening information transferred from Spruce Biosciences Study SPR001-203 to this study) will be used to determine eligibility and fulfill screening requirements for this study.

In Germany, screening information from Spruce Biosciences Study SPR001-203 is not permitted to be transferred to determine study eligibility.

A 6- or 12-week *Glucocorticoid Conversion Period* (Week -12 to either Week -6 or Week -2 [\pm 3 days]) for subjects on dexamethasone at the initial Screening Visit who agree to convert to a non-dexamethasone regimen as determined by their physician ([Section 1.3.3](#))

- A 76-week, 2-part *Treatment Period*
 - The 24-week *Placebo-Controlled Treatment Period* (Day 1 to Week 24) will be randomized, double-blind, and placebo-controlled. Subjects will be randomized in a 1:1 ratio to receive either placebo or tildacerfont at 200 mg QD.
 - The 52-week *Open-Label Period* (day after Week 24 to Week 76) will provide subjects who complete the Placebo-Controlled Treatment Period with 52 weeks of open-label treatment with tildacerfont 200 mg QD.
 - Beginning at Week 2 (based on the Day 1 A4 measurement), subjects with an A4 measurement \leq ULN at a study visit will begin to reduce their daily GC dose by increments of no more than 5 mg/day HCe each time, down to a minimum of 15 mg HCe per day. Beginning at Week 6 (based on Week 6 A4 measurement), subjects with an A4 $>$ 1.25x ULN will begin to increase their daily GC dose by increments of no more

than 5 mg/day HCe each time. More details on GC dose adjustments are provided in [Section 4.1.4.3](#).

- Subsequent GC dose adjustments are based on A4 measurements at Weeks 12, 18, 24, 32, 40, 52 and 64.
- For subjects continuing into the optional Open-Label Extension Period
 - The Open-Label Extension Period will provide subjects with up to 240 weeks of treatment with tildacerfont 200 mg QD.
 - Subjects will be eligible to adjust GC dose level at each visit (see [Section 4.1.4.3](#)).
- A 30-day *Follow-up Period at EOT*
 - Subjects who do not continue to the Open-Label Extension Period upon completion of Treatment Period will enter a 30-day Follow-up Period.

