4.1.2.3 Telephone Contacts

Sites will make scheduled telephone contacts during the Glucocorticoid Conversion Period at Weeks -11 and -6 (and -5, if applicable) and during the Treatment Period at Weeks 27 and 46 to record any AEs and concomitant medications.

After receiving A4 results from the Day 1 (dose reduction only) and Week 6, 12, 18, 24, 32, 40, 52, and 64 study visits, or during the optional Open-Label Extension Period, sites will make telephone contacts to subjects who are eligible for a GC dose adjustment. Sites will contact these subjects within 2 weeks after each applicable study visit. The site will direct the subject to adjust his/her GC dose at that time if the subject has not experienced any change in clinical status since the previous study visit. If no GC dose adjustment is warranted based on the A4 level, the site does not need to contact the subject. If a subject's GC dose is adjusted, the site will telephone the subject again 7 days after the GC dose adjustment to assess for the occurrence of AEs and the initiation of new concomitant medications.

Subjects should be instructed to telephone sites if they have any concerns about their health.

PRN telephone contacts initiated by sites and telephone contacts initiated by subjects should be captured in the EDC system as "unscheduled" telephone contacts.

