4.3.1.2 Glucocorticoid Dose Process and Documentation

Documentation of GC doses will be completed using eCRFs. If an adjustment in GC dose or change in distribution of daily doses is warranted, a new record will be recorded on the Prior and Concomitant Daily Glucocorticoids/Mineralocorticoids eCRF for each change.

At Weeks 24, 52 and 76 the eCRFs will record the total daily prescribed GC dose and will serve as the source for the Primary Efficacy Endpoint and GC-related change endpoints. For example, the recorded GC dose at Week 12 and the A4 assessment taken at Week 12 will be used to meet the Primary Efficacy Endpoint definition.

Based on the A4 assessment from each visit and aligning with the primary investigator's clinical judgement, the primary investigator will confirm if the GC dose level will be adjusted or maintained until the next clinic visit. For every visit with a potential adjustment in GC, the Key Glucocorticoid Dosing eCRF will record the A4 algorithm outcome (decrease, increase, maintain dose), whether the PI followed the algorithm's outcome (yes, no), reason for not following the outcome (clinical judgement, subject at physiologic dose), and the PI final decision (decrease, increase, maintain dose).

For subjects enrolled under protocol amendment 6 or earlier and prior to Week 24, the RTSM system will dispense a new GC regimen. For subjects enrolled under or after protocol amendment 7 or for visits after Week 24 for subjects enrolled under protocol amendment 6 or earlier, a new prescription will be written by the PI for the adjusted daily GC dose regimen and relayed to the subject to fill at their local pharmacy. An eCRF Glucocorticoid Medication – Received will record the date the subjects received/filled the new Sponsor-provided GC regimen and the day of first dose from the new regimen.

Reconciliation across eCRFs will be performed to ensure the accuracy of the GC dose data.

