⁸ Bottles of HC for stress dosing will be dispensed starting at the beginning of the Glucocorticoid Conversion Period and thereafter as needed to replace opened bottles. Accountability for bottles of HC will be performed at every study visit.

⁹ Subjects will use an electronic study diary to document background GC adherence. Female subjects will also use the study diary to record menstrual information (including start and stop dates of menses).

Table 3 Study SPR001-204 Protocol Schedule of Treatment Period and Follow-up Activities

STUDY VISIT NUMBER	Treatment Period												Follow-up ¹	ET
	Placebo-Controlled Treatment Period						Open-Label Period							
5 Base line	6	7	8	9	10		11	12		13	14	15	16	
STUDY WEEK	0	3	6	12	18	24	27	32	40	46	52	64	76	80
STUDY DAY ²	1	22	43	85	127	169	190	225	281	323	365	449	533	Last dose +30 days
Study Visit (V) / Telephone Contact (T) ³	V	V ⁴	V	V	V	V	T	V	V	T	V	V	V	V
Urine pregnancy test for FCP	X		X	X	X			X	X		X	X	X	X
Hormones from blood ^{5,6}	X		X	X	X			X	X		X	X	X	X
Clinical laboratory ^{5,7}	X	X	X	X	X			X	X		X	X	X	X
Urinalysis ⁵	X					X					X		X	X
HbA1c, fasting glucose and insulin, HOMA-IR ⁵	X					X					X		X	X

¹ Subjects who do not continue to the optional Open-Label Extension Period upon completion of the Treatment Period will enter a 30-day Follow-up Period.

² All study visits and telephone contacts should be performed on the indicated study days. In cases where adherence to the foregoing schedule is not possible, all activities for study visits and telephone contacts must be completed within a +6-day window after the indicated study days. The day of the baseline visit (and first dose of study drug) will be considered Day 1 (Week 0), and all other study days are counted relative to Day 1. There is no Day 0 (ie, study days go directly from Day -1 to Day 1).

³ During scheduled telephone contacts, sites will record any AEs and concomitant medications. After receiving A4 results during the Treatment Period, sites will make telephone contacts to applicable subjects regarding GC dose adjustment (detailed later in this Schedule of Activities). Subjects should be instructed to telephone sites if they have any concerns about their health. Telephone contacts initiated by sites and telephone contacts initiated by subjects should be captured in the EDC system as “unscheduled” telephone contacts.

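### The Week 24 analysis window has no cut-off at the switch to open-label drug, so a few Week 24 measurements could be values taken after tildacerfont has started

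*SAP*

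**What the plan says.** SAP 8.4 assigns values to visits by day: "instead of relying solely on visit labels in the clinical database, analysis visits and their windows are defined using Enrollment Day or Study Day". Within a window, "assessments and/or measurements will be flagged based on the collection date/time that is closest to the protocol-scheduled time point". The two relevant rows of Table 12 (visit, target, start, stop) read "Visit 10 Week 24 Study Day 169 149 197" and "Visit 11 Week 32 Study Day 225 198 253".

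Protocol 4.1.1 sets when the Open-Label Period runs and who enters it: "day after Week 24 to Week 76) will provide subjects who complete the Placebo-Controlled Treatment Period". Everyone in that period receives tildacerfont. After the Week 24 A4 result, GC may be changed by telephone. On timing, Protocol 4.1.2.3 says: "Sites will contact these subjects within 2 weeks after each applicable study visit". The visit schedule reproduced in SAP Table 3 says that activities "must be completed within a +6-day window after the indicated study days".

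The GC dose has its own source, a visit record. SAP 4.3.1.2 states: "the eCRFs will record the total daily prescribed GC dose and will serve as the source for the Primary Efficacy Endpoint". That rule applies to Week 24 and to two later visits.

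**The concern.** A window bounded by the midpoint to the next visit is reasonable when both visits fall in the same treatment period. Here the midpoint rule spans the planned change from placebo to active drug. Under the text as written, a placebo subject's value taken on tildacerfont can stand as that subject's double-blind Week 24 result.

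The three secondary endpoints are at stake. They are tested with Hochberg control if the primary is met (SAP 9.6), and A4 or cardiovascular measurements decide response in each. The treatment-policy estimand does not cover the case: SAP 12.3.1 lists the intercurrent events to be ignored, and the planned switch to open-label drug is not among them.

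**Working it through.** **1. Reproduce the window.** The target days in Table 12 are 127 (Week 18), 169 (Week 24) and 225 (Week 32).
- Week 18 stop: (127 + 169)/2 = 148, so Week 24 starts on Day 149.
- Week 24 stop: (169 + 225)/2 = 197, as stated.
- Length: 197 − 149 + 1 = 49 days, with 20 before target and 28 after.

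The same midpoint rule, rounded down, gives every stated stop day from Week 3 to Week 64. Day 197 therefore comes from visit spacing alone.

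**2. Overlay the switch and the GC call.**

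| Week 24 visit | First open-label day | Open-label days left in window | Last day for GC call | Window days after that |
|---|---|---|---|---|
| Day 169 | 170 | 197 − 169 = 28 | 169 + 14 = 183 | 197 − 183 = 14 |
| Day 175 (169 + 6) | 176 | 197 − 175 = 22 | 175 + 14 = 189 | 197 − 189 = 8 |

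Study drug is taken between 6 PM and midnight, so an 8 AM sample on the first open-label day still precedes the first open-label dose.

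**3. Apply the closeness rule.** A later value on Day u displaces a visit value on Day v when |u − 169| < |v − 169|.
- Valid value on Days 169 to 175: every later day is further from target, so no displacement is possible.
- Valid value on Day 155 (distance 14): any value on Days 156 to 182 displaces it. Days 170 to 182 are also past that visit's GC call limit (155 + 14 = 169).
- Valid value on Day 160 (distance 9): any value on Days 161 to 177 displaces it.
- No valid value at the visit: a single later value up to Day 197 is used.

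**4. Identify routes to a late value.**
- SAP 9.3.2 replaces an invalidated laboratory sample with a retest and sets no date limit.
- Protocol 11.2 has missed in-clinic activities, with DXA and scrotal ultrasound as its examples, made up at an unscheduled visit.
- SAP 8.4 itself expects visits outside the protocol windows, which includes early ones.

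**5. Look for a rule that blocks it.** None was found in SAP 8.3.18, 8.4, 9.3 or 12.3 to 12.5. SAP 8.3.9.2 does cut at the first tildacerfont dose, but only to define the tildacerfont baseline. SAP 8.3.18 labels a record with the drug being taken at the time, but does not remove it from the Week 24 window.

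**6. Size per subject.** With the planned 45 per group, one reclassified responder moves an arm's rate by 1/45 = 2.2 percentage points. The weight is larger in 2.2 (baseline dose ≤35 mg) and 2.3 (at least one baseline risk factor), because their denominators are subsets.

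**The case against.** Four objections limit the point, and all four stand.

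- **Few values can enter.** Table 12 is restricted by its title to clinic visits. No clinic visit is scheduled between Week 24 and Week 32, as Week 27 is a telephone contact. A valid value on Days 169 to 175 cannot be displaced. However, the title does not clearly exclude unscheduled clinic visits, so the routes in step 4 remain open.
- **A late Week 24 visit is not itself contaminated.** Open-label drug follows completion of the placebo-controlled period. Protocol 4.1.4.4 delays laboratory draws after stress dosing, and the wide upper bound usefully keeps such double-blind values. Comparing 28 days with the 6-day allowance therefore does not measure contamination.
- **The primary endpoint draws on a visit-specific record.** A reader might infer that an extra GC step of up to 5 mg/day, the same size as the 5 mg/day difference in SAP section 6, enters the primary result. The documents do not support that. The Week 24 dose is the prescribed dose on the Week 24 eCRF, not whichever record lies nearest Day 169. A 5 mg/day step in one subject is also not a 5 mg/day shift in a group mean.
- **A missing A4 and an algorithm-driven GC step do not normally coincide.** The step needs a valid Week 24 A4. A repeat A4 after an invalid one would usually follow some active drug but no new GC step. Where A4 was valid and a cardiovascular measurement is late, both may have occurred, though GC dose is not a component of 2.3.

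One gap remains on the primary. SAP 4.3.1.2 does not say that the Week 24 dose is the dose before the Week 24 A4 adjustment, and its worked example uses Week 12.

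**Conclusion.** The concern holds in limited form. As written, SAP 8.4 allows a post-switch value to be flagged as Week 24 when the on-visit value is missing, invalid, made up later or early. The exposed data are A4 in 2.1 and 2.2, the risk factors in 2.3, HOMA-IR, DXA and TART volume. For a Day 169 visit the exposed stretch is 28 of 49 days.

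The documents give no frequency. It is probably low, given how few assessments fall in that stretch. The direction is not fixed: GC can go up or down after Week 24, and for placebo subjects the late value also follows active drug. General contamination of the primary endpoint is not shown.

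The conclusion assumes that Table 12 applies to unscheduled clinic assessments and that no document outside the protocol and SAP sets a cut-off. The correction is worth making before unblinding because the endpoints exposed include those under formal error control.

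**What to change.** Add to SAP 8.4: for subjects who enter the Open-Label Period, the Week 24 window ends at the earlier of Day 197 and the first open-label dose. Only assessments taken before that dose may be flagged as Week 24, and later values are treated as missing for the placebo-controlled comparison. Subjects who never enter the Open-Label Period keep the full window, so off-drug data needed for treatment policy are retained. A late visit before the switch, up to Day 197, also still counts.

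Add to SAP 4.3.1.2: the Week 24 GC dose is the dose in force at the visit, before any change made on the Week 24 A4.

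No new data are needed, since SAP 8.3.4 and 8.3.9.2 already use the first tildacerfont dose date. The cost is a few more missing values. For 2.1 to 2.3 these go to the imputation in SAP 12.5.1.2. In the supportive definitions 2.3A and 2.3C, and in the adrenal biomarker responder table, missing counts as non-response. For the other exploratory endpoints imputation is optional.
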